### 4. STUDY DESIGN

#### 4.1. Overall Design

This is a Phase 1 randomized, crossover study in healthy participants to estimate the rBA of abrocitinib oral suspension (Test formulation) compared to commercial abrocitinib tablet

(Reference formulation) under fasted condition. The effect of ARA on the BA of abrocitinib and its metabolites will be evaluated by administering abrocitinib 200 mg commercial tablet with or without famotidine 40 mg as an ARA. Part B is to assess the taste and palatability of 6 different abrocitinib oral suspension formulations, to guide the selection and development of abrocitinib pediatrics oral suspension formulation.

CCI

This study consists of 2 parts, as listed below.

**Part A:** This part of the study will be an open label, randomized, single dose, crossover, 3-treatment, 6-sequence, 3-periods design. Approximately 18 healthy male and/or female participants (18-55 years) will be enrolled and randomized to 1 of 6 possible treatment sequences. Participants who discontinue from the study may be replaced at the sponsor's discretion. The replacement participant will receive the same treatment sequences as the participant who discontinued. Each randomized treatment sequence will consist of 3 treatment periods as shown in Table 4.

**Table 4. Randomized Treatment Sequences of Part A**

Sequence	Period 1	Period 2	Period 3
1 (n=3)	A	B	C
2 (n=3)	B	C	A
3 (n=3)	C	A	B
4 (n=3)	A	C	B
5 (n=3)	B	A	C
6 (n=3)	C	B	A

Treatment A = Abrocitinib 200 mg commercial tablet only, under fasted conditions.

Treatment B = Abrocitinib 200 mg oral suspension formulation 1, under fasted conditions.

Treatment C = Famotidine 40 mg tablet administered 2 hours prior to abrocitinib 200 mg commercial tablet under fasted conditions.

Healthy participants will be screened within 28 days prior to the first administration of the study intervention to confirm that they meet the participant selection criteria for the study. Eligible participants will be admitted to the CRU on Day -1 and will be confined in the CRU until Discharge, which is Day 2 of Period 9, in Part B of the study (SoA), after completing both Parts A and B of the study. Day -1 is defined as the day prior to the first day of dosing (Day 1).

In Period 1 through Period 3 of Part A, participants will receive a single 200 mg dose of abrocitinib commercial tablet (Treatment A), a single 200 mg dose of abrocitinib oral suspension (Treatment B), or 40 mg famotidine tablet administered 120 minutes prior to a single dose of 200 mg dose of abrocitinib commercial tablet (Treatment C) after a fast of at least 10 hours before taking the study intervention, abrocitinib. All participants will be fasting for at least 10 hours before taking abrocitinib. CCI

CCI

**Part B:**

Participants who complete Part A of the study are expected to proceed to Part B. Part B will be a single-blind, randomized, 6-period, cross-over study in healthy male and/or female adult participants (18-55 years). A total of 18 healthy participants will be enrolled and randomized to 1 of 6 possible treatment sequences. Participants who discontinue from the study may be replaced at the sponsor's discretion. The replacement participant will receive the same treatment sequences as the participant who discontinued. Each randomized treatment sequence will consist of 6 treatment periods (Table 5).

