#### Randomized Treatment Sequences of Part B

Sequence	Period 4	Period 5	Period 6	Period 7	Period 8	Period 9
1 (n=3)	F1+ARA	F2+ARA	F3+ARA	F4+ARA	F5+ARA	F6+ARA
2 (n=3)	F6+ARA	F1+ARA	F2+ARA	F3+ARA	F4+ARA	F5+ARA
3 (n=3)	F5+ARA	F6+ARA	F1+ARA	F2+ARA	F3+ARA	F4+ARA
4 (n=3)	F4	F5	F6	F1	F2	F3
5 (n=3)	F3	F4	F5	F6	F1	F2
6 (n=3)	F2	F3	F4	F5	F6	F1

F1 = Abrocitinib oral suspension formulation 1 under fasted conditions.

F2 = Abrocitinib oral suspension formulation 2 under fasted conditions.

F3 = Abrocitinib oral suspension formulation 3 under fasted conditions.

F4 = Abrocitinib oral suspension formulation 4 under fasted conditions.

F5 = Abrocitinib oral suspension formulation 5 under fasted conditions.

F6 = Abrocitinib oral suspension formulation 6 under fasted conditions.

ARA = Famotidine 40 mg under fasted condition.

Abrocitinib oral suspension formulations 1 to 6 for tasting will be offered to all participants in a blinded fashion. Participants randomized to Sequence 1-3 will receive famotidine (40 mg with 240 mL of room temperature water) 120 minutes before administering a single 200 mg dose of abrocitinib oral suspension formulations 1 to 6 with participants fasting for at least 10 hours before taking abrocitinib. While participants randomized to Sequence 4-6 will receive abrocitinib oral suspension formulations 1 to 6 with participants fasting for at least 10 hours before taking abrocitinib. Participants will place samples into their mouths, swish the sample in the mouth for approximately 10 seconds and then swallow it. Each participant

PFIZER CONFIDENTIAL

will record the sensory attributes at timed intervals of 0 (immediately after dosing), 5, 10, and 20 minutes after swallowing using the abrocitinib Taste Assessment Questionnaire. Each formulation will be tested daily. Participants will be asked as much as possible not to verbalize their responses and not discuss taste with other participants until after they have filled out the response for that formulation in the questionnaire. Participants will cleanse their mouths with room temperature water before tasting a formulation. This water will not be swallowed.

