**Table 5. Randomized Treatment Sequences of Part B**

Sequence	Period 4	Period 5	Period 6	Period 7	Period 8	Period 9
1 (n=3)	F1+ARA	F2+ARA	F3+ARA	F4+ARA	F5+ARA	F6+ARA
2 (n=3)	F6+ARA	F1+ARA	F2+ARA	F3+ARA	F4+ARA	F5+ARA
3 (n=3)	F5+ARA	F6+ARA	F1+ARA	F2+ARA	F3+ARA	F4+ARA
4 (n=3)	F4	F5	F6	F1	F2	F3
5 (n=3)	F3	F4	F5	F6	F1	F2
6 (n=3)	F2	F3	F4	F5	F6	F1

F1 = Abrocitinib oral suspension formulation 1 under fasted conditions.

F2 = Abrocitinib oral suspension formulation 2 under fasted conditions.

F3 = Abrocitinib oral suspension formulation 3 under fasted conditions.

F4 = Abrocitinib oral suspension formulation 4 under fasted conditions.

F5 = Abrocitinib oral suspension formulation 5 under fasted conditions.

F6 = Abrocitinib oral suspension formulation 6 under fasted conditions.

ARA = Famotidine 40 mg under fasted condition.

For any new healthy participants joining Part B only to support the achievement of the total number of 18 healthy participants enrolled or randomized in this part of the study, screening for healthy participants will be performed within 28 days prior to the first administration of the study intervention to confirm that they meet the participant selection criteria for the study.

Abrocitinib oral suspension formulations 1 to 6 for tasting will be offered to all participants in a blinded fashion. Participants randomized to Sequence 1-3 will receive famotidine (40 mg with 240 mL of room temperature water) 120 minutes before administering a single 200 mg dose of abrocitinib oral suspension formulations 1 to 6 with participants fasting for at least 10 hours before taking abrocitinib. While participants randomized to Sequence 4-6 will receive abrocitinib oral suspension formulations 1 to 6 with participants fasting for at least 10 hours before taking abrocitinib.

For participants receiving the ARA, famotidine, a 40 mg dose of famotidine tablet will be administered 2 hours before administering the study intervention with participants fasting for at least 10 hours before taking abrocitinib.

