inhibitor of H2 receptors which inhibits both basal and nocturnal gastric secretion. After oral administration of famotidine, the onset of the antisecretory effect occurred within 1 hour; the maximum effect was dose-dependent, occurring within 1 to 3 hours. Intragastric pH after a single dose of famotidine 40 mg was shown to rapidly increase to pH >4.0 within 2 hours of administration, with a duration of inhibition of secretion lasting for 10 to 12 hours. In the present study, the maximum allowed dose of famotidine, famotidine 40 mg, will be administered 2 hours before abrocitinib to achieve its maximal acid-reducing and pH-increasing effects. This dose was selected to align with the FDA guidance stating that sponsors should select the maximum recommended dose of an ARA to characterize the worst-case scenario possible.

**Part B:** In Part B, treatments will be presented to the participants in a blinded fashion to minimize the potential bias for taste evaluation.

CCI

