### 6.1.1. Administration

**Part A:** Following an overnight fast of at least 10 hours, participants will receive the study intervention, abrocitinib, at approximately 0800 hours (plus or minus 2 hours). Investigator site personnel will administer the study intervention during each period with ambient temperature water to a total volume of approximately 240 mL. Participants will swallow the study intervention whole and will not manipulate or chew the study intervention prior to swallowing. For participants receiving the ARA, famotidine, a 40 mg dose of famotidine tablet will be administered 2 hours before administering the study intervention, abrocitinib, with participants fasting for at least 10 hours before taking abrocitinib.

**Part B:** Abrocitinib oral suspension formulations 1 to 6 for tasting will be offered to all participants in a blinded fashion. Following an overnight fast of at least 10 hours, participants will receive the study intervention, abrocitinib, at approximately 0800 hours (plus or minus 2 hours). Participants will place samples into their mouths, swish the sample in the mouth for approximately 10 seconds and then swallow it. Each participant will record the sensory attributes at timed intervals of 0 (immediately after dosing), 5, 10 and 20 minutes after swallowing using the Abrocitinib Taste Assessment Questionnaire. Each formulation will be tested daily. Participants will be asked as much as possible to not verbalize their responses and not discuss taste with other participants until after they have filled out the response for that formulation in the questionnaire. Participants will cleanse their mouth with room temperature water before tasting a formulation. This water will not be swallowed. For participants receiving the ARA, famotidine, a 40 mg dose of famotidine tablet will be administered 2 hours before administering the study intervention with participants fasting for at least 10 hours before taking abrocitinib.

For both Part A and Part B of the study, participants will be instructed to fast for at least 10 hours before receiving abrocitinib. Water will be withheld for 1-hour predose and 1 hour after study treatment administration, and food will only be allowed after 4 hours postdose.

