[figure not shown]
while Treatment B (Abrocitinib suspension) and Treatment C (Abrocitinib tablet + famotidine) are the Test Treatments.

For the taste assessment in Part B of the study, the data used in the analysis will be transcribed and rescaled to a score from 0 to 100 from the raw measurements on the questionnaire. The sensory attributes (overall liking, mouthfeel, bitterness, sourness, saltiness, tongue/mouth burn) from the taste questionnaires ([Appendix 8](#)) will be listed and descriptively summarized by prototype formulation, and question across participants. Summary statistics (mean and 90% CI) will be calculated for the various questions. Radar plots for each of 4 time points, summarizing all attributes for each treatment will be generated. Boxplots of each attribute will be plotted against the time points.

[figure not shown]
[figure not shown]
[figure not shown]

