## **10. SUPPORTING DOCUMENTS AND OPERATIONAL CONSIDERATIONS**

### **10.1. Appendix 1: Regulatory, Ethical, and Study Oversight Considerations**

#### **10.1.1. Regulatory and Ethical Considerations**

This study will be conducted in accordance with the protocol and with the following:

- Consensus ethical principles derived from international guidelines, including the Declaration of Helsinki and CIOMS International Ethical Guidelines;
- Applicable ICH GCP guidelines;
- Applicable laws and regulations, including applicable privacy laws.

The protocol, protocol amendments, ICD, SRSD(s), and other relevant documents (eg, advertisements) must be reviewed and approved by the sponsor, submitted to an IRB/EC by the investigator, and reviewed and approved by the IRB/EC before the study is initiated.

Any amendments to the protocol will require IRB/EC approval before implementation of changes made to the study design, except for changes necessary to eliminate an immediate hazard to study participants.

Protocols and any substantial amendments to the protocol will require health authority approval prior to initiation except for changes necessary to eliminate an immediate hazard to study participants.

The investigator will be responsible for the following:

- Providing written summaries of the status of the study to the IRB/EC annually or more frequently in accordance with the requirements, policies, and procedures established by the IRB/EC;
- Notifying the IRB/EC of SAEs or other significant safety findings as required by IRB/EC procedures;
- Providing oversight of the conduct of the study at the site and adherence to requirements of 21 CFR, ICH GCP guidelines, the IRB/EC, European regulation 536/2014 for clinical studies (if applicable), European Medical Device Regulation 2017/745 for clinical device research (if applicable), and all other applicable local regulations.

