Participants who complete Part A of the study are expected to proceed to Part B. Part B will be a single-blind, randomized, 6-period, cross-over study in healthy male and/or female adult participants (18-55 years). A total of 18 healthy participants will be enrolled and randomized to 1 of 6 possible treatment sequences. Participants who discontinue from the study may be replaced at the sponsor's discretion. The replacement participant will receive the same treatment sequences as the participant who discontinued. Each randomized treatment sequence will consist of 6 treatment periods (Table 2).

Table 2. Randomized Treatment Sequences of Part B

Sequence	Period 4	Period 5	Period 6	Period 7	Period 8	Period 9
1 (n=3)	F1+ARA	F2+ARA	F3+ARA	F4+ARA	F5+ARA	F6+ARA
2 (n=3)	F6+ARA	F1+ARA	F2+ARA	F3+ARA	F4+ARA	F5+ARA
3 (n=3)	F5+ARA	F6+ARA	F1+ARA	F2+ARA	F3+ARA	F4+ARA
4 (n=3)	F4	F5	F6	F1	F2	F3
5 (n=3)	F3	F4	F5	F6	F1	F2
6 (n=3)	F2	F3	F4	F5	F6	F1

F1 = Abrocitinib oral suspension formulation 1 under fasted conditions.

F2 = Abrocitinib oral suspension formulation 2 under fasted conditions.

F3 = Abrocitinib oral suspension formulation 3 under fasted conditions.

F4 = Abrocitinib oral suspension formulation 4 under fasted conditions.

F5 = Abrocitinib oral suspension formulation 5 under fasted conditions.

F6 = Abrocitinib oral suspension formulation 6 under fasted conditions.

ARA = Famotidine 40 mg under fasted condition.

For any new healthy participants joining Part B only to support the achievement of the total number of 18 healthy participants enrolled or randomized in this part of the study, screening for healthy participants will be performed within 28 days prior to the first administration of the study intervention to confirm that they meet the participant selection criteria for the study.

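### Part B's cyclic sequence table gives each suspension one fixed predecessor in 15 of 18 participants; a Williams square of the same size would spread predecessors evenly

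*Protocol*

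**What the plan says.** Protocol 4.1 (Part B) states: "A total of 18 healthy participants will be enrolled and randomized to 1 of 6 possible treatment sequences". Table 5, repeated in the Synopsis and as Table 2 in SAP 2.1, lists six orders with three participants each. Row 1 runs F1 to F6, and every later row is the same cycle started at another formulation. The acid-reducing agent (ARA) is tied to the row number: "Participants randomized to Sequence 1-3 will receive famotidine (40 mg with 240 mL of room temperature water) 120 minutes before" the suspension, while Sequences 4-6 take the suspension alone.

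The stated protections are blinding (Protocol 4.2: "treatments will be presented to the participants in a blinded fashion to minimize the potential bias for taste evaluation"), one formulation per day after an overnight fast, and a rinse (Protocol 6.1.1: "Participants will cleanse their mouth with room temperature water before tasting a formulation").

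For the analysis, Protocol 9.3.2.1.2 says the attributes will be "descriptively summarized by prototype formulation, and question across participants. Summary statistics (mean and 90% CI) will be calculated for the various questions". SAP 8.2 plans the same summaries, and SAP 6.4 lists no covariates. The visible text gives no model, period term or carryover term for taste. The mixed model shown is for the Part A PK parameters.

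**The concern.** A taste rating can depend on what was tasted last, either through residual taste or through comparison with the previous day's sample. Table 5 balances formulations over periods but not over predecessors. F2 almost always follows F1, F3 follows F2, and so on round to F1 following F6. If one formulation is unusually unpleasant or unusually mild, its effect on the next rating falls almost entirely on one competitor.

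Taste is the primary Part B objective. It is meant to guide selection of the pediatric suspension and to inform whether taste masking is needed. An effect that lands on one formulation and spares four others can reorder those five. Part A does not have this weakness: Table 4 uses all six orders of three treatments, so each ordered pair occurs twice, despite a 72-hour washout.

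**Working it through.** **Inputs.** Rows of Table 5; n = 3 per row; unadjusted mean per formulation (Protocol 9.3.2.1.2, SAP 8.2); rating scale 0-100. The size of a predecessor effect is not in the documents; 10 points is assumed, with a range of 5-15.

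**Step 1: the plan's own figure.** 6 sequences × 3 = 18 participants, as stated.

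**Step 2: period balance.** Each formulation is in each of Periods 4-9 in exactly 3 participants, so a common period effect cancels over the six rows.

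**Step 3: predecessors.** Six formulations give 6 × 5 = 30 ordered pairs. Table 5 contains only six (F1→F2, F2→F3, F3→F4, F4→F5, F5→F6, F6→F1), each in 5 rows, that is 5 × 3 = 15 participants. In the other 3 the formulation opens Part B. A 6 × 6 Williams square contains all 30 pairs once, so each predecessor applies in 3 of 18.

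**Step 4: what enters the unadjusted mean.** Let λ(j) be the shift that formulation j causes in the next rating.

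- Table 5: shift in the mean of i = (15/18) λ(predecessor of i) = (5/6) λ(predecessor of i).
- Williams: shift in the mean of i = (3/18) × the sum of λ over the other five, that is 1/6 of each.

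The total predecessor weight is 5/6 in both designs, since 5 × 1/6 = 5/6. A shift common to all six therefore cancels in every contrast under either design. For unequal shifts, the bias in the contrast i − k is (5/6)[λ(pred i) − λ(pred k)] under Table 5 and (1/6)[λ(k) − λ(i)] under Williams.

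**Step 5: size if only F1 has an effect.**

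| Assumed λ(F1) | Table 5: F2 mean | Table 5: other means | Williams: each of F2-F6 |
|---|---|---|---|
| 5 | 5 × 5/6 = 4.2 | 0 | 5/6 = 0.8 |
| 10 | 10 × 5/6 = 8.3 | 0 | 10/6 = 1.7 |
| 15 | 15 × 5/6 = 12.5 | 0 | 15/6 = 2.5 |

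Under Williams, contrasts among F2-F6 are untouched.

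**Step 6: precision.** Fit participant + period + formulation, with and without a first-order carryover term, and take the variance of a pairwise formulation contrast in units of σ².

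| Setting | Table 5 | Williams rows proposed below |
|---|---|---|
| All 18, no carryover term | 0.111 | 0.111 |
| All 18, carryover term | 0.806 | 0.115 |
| One ARA half (9), no carryover term | 0.261-0.350, mean 0.299 | 0.250-0.292, mean 0.283 |
| One ARA half, carryover term | rank 21 of 24; 3 of 15 contrasts estimable (0.820-0.828) | rank 24; 15 of 15 estimable (with ARA 0.388-1.616, mean 0.825; without ARA 0.437-1.814, mean 0.896) |

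Over all rows the carryover-adjusted ratio is 0.806/0.115 = 7.0.

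**Step 7: period position by ARA group.** Under Table 5, F1 has mean period position 2 with ARA and 5 without, a gap of 3.0. This is the largest gap; the average over formulations is 1.67. Under the proposed rows the largest is 1.67 and the average 1.0.

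**The case against.** The strongest reply is that no harm has been shown. Daily spacing, the fast, the rinse and blinding all work against residual taste. What is left is mainly a contrast or expectation effect across about a day, and nothing in the documents gives its size. The 5-15 point range is an assumption, and zero is possible. This stands, and it keeps the point at the level of an inexpensive improvement.

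Only unequal predecessor effects matter, and a Williams mean carries the same total predecessor weight. Both statements are correct. The gain is in how the weight is spread.

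The sevenfold variance figure belongs to a carryover model that the visible plan does not contain; without that term the designs are equally precise. That also stands. The figure shows only that adjusting afterwards would be costly under Table 5. Likewise, some within-half contrasts under the proposed rows remain imprecise once carryover is modelled.

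The SAP sets no decision rule, and the title of Protocol Table 10 frames Part B as precision of each mean rather than a ranking test. Even so, the stated purpose is to guide selection among six products, which means comparing their means.

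Participants coming from Part A have already taken Formulation 1, some in Period 3, so opening Part B does not mean no prior exposure. Neither design balances this. Finally, part of the Part B design rationale and the formulation compositions are redacted, so a justification for the order may exist unseen.

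None of this alters the predecessor counts or makes Table 5 preferable to a balanced square of the same size.

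**Conclusion.** The concern holds as a conditional statement. Table 5 fixes one predecessor per formulation in 15 of 18 participants, and the planned unadjusted means would retain 5/6 of any differential effect of that predecessor on a single competitor. Under the assumed 10-point shift (5-15) from one formulation, that is 8.3 points (4.2-12.5) on one mean, against 1.7 (0.8-2.5) spread equally over five under a Williams square.

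This rests on an additive, first-order effect whose existence and size the documents do not give, and on the visible taste analysis being the whole of it. The change should be made because it costs no precision, participants or periods. Confidence is medium because the effect itself is unproven.

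**What to change.** Before Part B is randomized, replace the six rows of Table 5 with this Williams square, n = 3 per row:

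| Sequence | P4 | P5 | P6 | P7 | P8 | P9 |
|---|---|---|---|---|---|---|
| 1 (with ARA) | F1 | F2 | F6 | F3 | F5 | F4 |
| 2 (with ARA) | F2 | F3 | F1 | F4 | F6 | F5 |
| 3 (with ARA) | F4 | F5 | F3 | F6 | F2 | F1 |
| 4 (no ARA) | F3 | F4 | F2 | F5 | F1 | F6 |
| 5 (no ARA) | F5 | F6 | F4 | F1 | F3 | F2 |
| 6 (no ARA) | F6 | F1 | F5 | F2 | F4 | F3 |

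Every ordered pair occurs once, and every formulation occurs once per period.

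Keep this row order. If the square is listed cyclically (starting F1, F2, F3, F4, F5, F6) and alternate rows are given the ARA, odd and even formulations are confounded with period within each half: rank 18 where 19 is needed, and only 6 of 15 contrasts estimable. The square balances first-order carryover over all six rows. It does not remove carryover, and predecessors stay partly unbalanced within each ARA half.

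Cost: a new randomization list; the table replaced in the protocol Synopsis, Protocol 4.1 and SAP 2.1; and an amendment, since Protocol 10.1.1 states "Any amendments to the protocol will require IRB/EC approval before implementation of changes made to the study design". The text assigning famotidine to Sequences 1-3 stays correct. Participants, periods, products and the number of participants given famotidine do not change.
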